1.0 Objective

This study is designed to obtain preliminary data comparing indwelling pleural catheters (IPCs) versus IPCs plus doxycycline for pleurodesis as treatments for malignant pleural effusions (MPE).

- The primary outcome is time to pleural catheter removal.
- Secondary outcomes include assessment of symptom burden, pleurodesis efficacy, complications, health care resource utilization, need of hospitalization for pain control, pain free days and mortality

2.1 Rationale

Malignant Pleural Effusions:

MPEs occur in 7 to 15% of lung cancer cases and complicate the course of many other types of cancer.¹ In the United States, more than 156,000 new cases of MPE occur each year, with 75% of these being caused by lung and breast cancer^{1,2}. Patients usually present with dyspnea, initially on exertion and later at rest. This results in significant functional impairment and subsequent decrease in quality of life (QOL). Because MPE occurs in patients with advanced cancer, management is palliative, with the goal being to alleviate dyspnea and distress. Successful palliation is dependent on long-term relief of the symptoms that are caused by the MPE and prevention of pleural fluid re-accumulation.

Treatment Options:

Options for the management of MPE include (1) intermittent thoracentesis; (2) chest tube drainage followed by pleurodesis; (3) thoracoscopic drainage followed by pleurodesis; or (4) pleurodesis using long-term IPCs. It is useful in this context to identify the components of each management strategy.

The first component is some method of fluid drainage (i.e. thoracentesis or chest tube or catheter). The second component is whether or not a pleurodesis agent is used and if so what type. The pleurodesis agent can be talc or doxycycline or any of a variety of other agents that induce scarring and inflammation in the pleura to essentially prevent fluid recurrence. However, pleurodesis agents are not always utilized – i.e. in the intermittent thoracentesis and IPC strategy no pleurodesis agent is used. The evidence basis for choosing between these alternatives has significant gaps and limitations that are clinically important, since there are few randomized trials and most studies have relatively small sample sizes.

Given these limitations, meta-analysis^{3,4} suggested that use of chemical agents for pleurodesis was more effective than nothing, that talc was the most effective agent, and that talc insufflation via thoracoscopy was more effective than talc slurry via chest tube. However talc as a pleurodesis agent is associated with acute respiratory distress syndrome (ARDS) and thoracoscopy requires an inpatient stay of several days. A more recent large phase III intergroup trial suggested that talc insufflation via thoracoscopy was similar in efficacy to talc

slurry via chest tube, but both methods required a prolonged inpatients stay and both had

significant complications including ARDS (8% in the thoracoscopic talc group and 4% in the chest talc group).⁵ This led to questions regarding talc's safety, whether delivered by chest tube or thoracoscopy. In addition, the meta-analyses noted above^{3,4} did not include IPCs, so how IPCs compare to thoracoscopic pleurodesis is not as well studied.

IPCs (IPCs) were pioneered at M.D. Anderson. They have been shown to be effective in relieving dyspnea and improving QOL.^{1,6-8} The main complication is catheter infection, which is fairly uncommon and can usually be treated with outpatient antibiotics. Typically about two thirds of patients with IPCs will eventually have decreased drainage, usually several weeks to months after initial placement. Once drainage is minimal, the IPC is typically removed. This is done according to a standard management algorithm. Once removed, the fluid usually does not recur. Of note, IPCs management strategies have not typically involved the use of any pleurodesis agent, but rather pleurodesis is achieved "spontaneously" after prolonged drainage. In addition IPC's allow patients to be treated completely in the outpatient setting, which is a significant advantage compared to thoracoscopic and chest tube pleurodesis techniques. A recent randomized controlled trial of IPCs vs. chest tubes with talc slurry found no significant difference in terms of dyspnea relief at 42 days between the two groups, but dyspnea relief was better at 6 months in the IPC group.⁹ However, current evidence based guidelines are not definitive as to which approach is best.¹

As a result, based on the limited clinical evidence available, IPCs are now the dominant therapeutic option employed for management of MPE at MD Anderson. However, because of the absence of well-designed randomized clinical trials, little consensus exists at the national and international level as to the best procedure and as a result there is significant practice variation.^{10,11} For example, a survey of physician practice patterns demonstrated that the first-choice treatment of MPE in the community was chest tubes 75% of the time, video-assisted thoracoscopy 17% of the time, and medical thoracoscopy 8% of the time.¹⁰ In contrast, at M.D. Anderson, over 90% of outpatients receive IPCs, while inpatients may be treated with either thoracoscopy or indwelling catheters. The existence of this widespread variation is cause for concern because the different techniques probably vary in terms of effectiveness, risk, and cost.

Rationale and Significance:

In this context it is useful to quantify what the MDACC current standard of care is and how it performs, since that will be the comparator for this study. In this study the intervention will be IPC plus pleurodesis agent (doxycycline) and the comparator is the current standard of care, which is IPC alone. IPC performance has already been studied by our group previously.⁸ In a study of 266 patients undergoing IPC placement for MPE at MDACC, using a competing risk model, we found the 1-year cumulative incidence of events was: death with IPC in place, 35.7%; IPC removal due to decreased drainage, 51.9%; and IPC removal due to complications, 7.3%. Recurrent MPE requiring repeat intervention occurred in 14% of patients whose IPC was removed. Fluid recurrence was more likely if the catheter was removed because of complications (e.g. infection) than if it was removed due to decreased drainage ($p=0.04$).

The proposed study will be the first randomized trial to evaluate the combination of IPCs with a pleurodesis agent vs. conventional IPC management. This combination strategy offers significant potential advantages over existing strategies since it would allow patients with MPE to be managed completely as outpatients (something that cannot be done with chest tubes or thoracoscopic methods) while still allowing patients the benefits of a pleurodesis agent. The pleurodesis agent should shorten the time to pleural space closure, since it will induce more inflammation and fibrosis than conventional IPCs alone. Conventional IPCs (i.e. without any pleurodesis agent) rely upon spontaneous pleurodesis after prolonged drainage but that typically takes 2-4 months and it does not always occur.

We hypothesize that addition of a pleurodesis agent will allow earlier catheter removal. The benefit of earlier catheter removal is that it decreases the risk of infectious complications and saves money since each pack of drainage bottles costs about \$500. It also improves patient QOL.

Our secondary hypothesis is that addition of a pleurodesis agent will decrease the frequency of pleural fluid effusion recurrence requiring intervention in those that have their IPC removed. In our prior prospective observational study this occurred in 14% of cases.

While talc is more effective than doxycycline for pleurodesis, doxycycline does not have any ARDS risk. In addition, since one important goal is to manage patients with MPE completely in the outpatient setting, the risk of patients developing ARDS at home in an unmonitored setting is significant. When ARDS has developed in prior studies of talc pleurodesis, the patients were inpatients. Outcomes might be significantly worse if ARDS developed rapidly in a tenuous cancer patient at home. On balance, since this is a palliative intervention in patients that often have very limited pulmonary reserve, the risks associated with talc due to ARDS therefore outweigh the small marginal benefits in terms of fluid recurrence rates as compared to doxycycline.^{3,4} Doxycycline is widely available and has been used before for pleurodesis, so the methods could be easily replicated in other institutions and would potentially change the standard of care.

2.2 Hypothesis

Our hypothesis is that IPCs plus doxycycline will be superior to IPCs alone in terms of time to catheter removal. Our secondary hypothesis is that IPC plus doxycycline will be superior to IPCs alone in terms of recurrence of effusions requiring drainage after IPC removal.

3.1 Type of Subjects to be studied

Inclusion Criteria:

- 1) Outpatients with MPE undergoing IPC placement; 2) Age 18 or older; 3) Sufficient mental capacity to answer SF-6D and Borg score questions.

Exclusion Criteria:

- 1) Patients undergoing pleurodesis for benign disease (e.g., spontaneous pneumothorax); 2) Inability or unwillingness to give informed consent; 3) Inability to perform phone call and clinical follow-up at MDACC; 4) Previous intrapleural therapy for MPE on the same side;
- 5) Chylous effusions associated with malignant disease; 6) ECOG of 4 and life expectancy ≤ 2 weeks; 7) Doxycycline allergy 8) Contraindication to placement of an IPC (e.g., uncorrected coagulopathy)..

4.1 Research Plan and Methods

Study Design:

This is a double blind randomized controlled trial of patients with MPE undergoing IPC placement as part of their standard of care. The Clinical Oncology Research System (CORE) will be used to generate randomization. This will be done immediately after the subject has consented for the protocol.

The primary outcome will be time to pleural catheter removal. Secondary outcomes will include recurrence of effusion requiring drainage in patients that have their IPC removed. Other secondary outcomes will be quality adjusted survival (calculated using the SF-6D to determine utilities and then integrating utilities over time to arrive at quality-adjusted survival), change in

dyspnea (using the Borg score), IPC complications, procedure associated pain, and need for hospitalization due to pain from pleurodesis.¹²

Study Procedures:

The study will prospectively enroll patients being treated for MPE as part of their standard medical care. Note that all measurements are currently part of the standard of care. This includes measurements of QOL, which are captured on the SF-6D for all patients who come to pulmonary clinic. A total of 250 patients undergoing IPC treatment for MPE will be enrolled and randomized in a 1:1 ratio to either IPC + doxycycline or IPC alone. Following enrollment, the schedule of events will be as shown in Figure 1 below. We will obtain informed consent on all patients.

The study will be blinded to the patient and the long term clinical care management team. After initial consent at the time of IPC placement, research coordinators will arrange for a single extra visit to be made at day 5 +/- 2 for all patients. The reason for the 5 +/- 2 days is to allow patients to come during regular clinic hours rather than on weekends. During this additional visit a different physician team, called the pleurodesis team, will give patients either doxycycline or saline control via the IPC. This team is different than the team that will be making all clinical management decisions. The pleurodesis team will only be giving the drugs on day 5 and managing perioperative pain. In this way all management decisions as to catheter removal, complications, and other aspects of pleural effusion care will be made by the standard clinical care team who will be blinded as to the patient's study status. Patients that receive intrapleural pleurodesis agents, whether it is talc or doxycycline or other agents, sometimes have significant pain during the procedure. The standard of care is to control this with short acting narcotics. But we need to keep the management team blinded as to the use of these narcotics since that might bias their decision making.

A standardized pain control algorithm, developed in conjunction with the pain clinic, will be used. This is shown in figure 2 and this will be used by the pleurodesis team in conjunction with the pain management clinic in the perioperative period to control pain. We will assess pain using a VAS as well.

Subsequent visits will follow the current standard of care algorithms. This dictates how often the catheter is drained and when the catheter is removed and how infections and complications are dealt with. These are all in our current care pathways and will be carried out by the usual clinical team. These are shown in figures 3-5 and cover routine drainage (figure 3), malfunctions (figure 4), and infections (figure 5). Research coordinators will capture this data and do phone call follow-up after the catheters are removed in order to determine if fluid recurs. Patients will be followed for at least 1 year after IPC placement.

Data Collection and Confidentiality Procedures:

The data will be kept in a database on a password-protected computer in a secure office. This information will only be accessible to the study investigators and staff.

Statistical Considerations:

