We will seek Research-related patient care clinical charges funding (RPCCC) for the 2 patient visits that are not currently part of our standard of care. Pleurodesis for MPE is covered by all carriers and is part of the standard of care, the only part that is not part of the standard of care is the additional visit which is unnecessary for the control arm if this was the standard of care. All drugs and other aspects would be standard of care. The CPT code would be 99212.

Figure 1. Study flow chart

Outpatients with MPE eligible for IPC, consents to trial at time of IPC. There must be no evidence of extensive loculation or hydropneumothorax or other contraindication to pleurodesis or narcotics. IPC placed by “long term” team and a f/u with the pleurodesis team for day 5 +/- 2 is arranged by the research coordinator (Clinic visit with MLP and procedure)

Patient comes in on day 5 \pm 2 and is seen and treated by “pleurodesis team”

- Fentanyl patch 12 mcg/hr in AM. Comes in and gets CXR
- If ECOG \leq 2 AND patient is now an outpatient AND if patient is eligible for pleurodesis – defined as not tremendously loculated by ultrasound and no hydropneumothorax or severe pain after drainage of the effusion (defined as >2 points more than the pain experienced on first day of drainage) or small amount of fluid output despite large amount of fluid being present on CXR with estimated residual volume based on CXR and drainage volume being ≥ 500 ml or other contraindication to pleurodesis AND if there are no contraindications to narcotics then randomize.
- If patient is ineligible for randomization due to above items then take fentanyl patch off and managed as per usual standard of care.

[figure not shown]

Figure 2. Pain Control Algorithm for IPC
Indwelling pleural catheter pleurodesis Pain Control Algorithm.

1. Identify patient for IPC with pleurodesis and consent patient. Obtain baseline measures for Borg, SF6D, and pain instrument, as per usual standard. Consent patient for trial if pleurodesis is feasible (i.e. not tremendously loculated effusion and no hydropneumothorax or trapped lung or other contraindication to pleurodesis).
2. If patient consents schedule f/u appointment for day 5 +/- 2 at the time of IPC placement with pleurodesis team. This is a f/u visit with MLP with a procedure slot booked as well for same day (can be booked as IPC)

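### The text randomizes at consent, Figure 1 only after an eligibility check at day 5 ± 2; the two rules cannot both be followed

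*Combined protocol and SAP*

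**What the plan says.** **Timing.** Section 4.1, Study Design, has CORE generate the randomization and adds: "This will be done immediately after the subject has consented for the protocol". Study Procedures fixes when consent happens: "After initial consent at the time of IPC placement". Figure 1 also puts consent at catheter placement. Together these put allocation several days before the study agent is given.

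Figure 1 gives a different order. At the day 5 ± 2 visit it lists conditions to be met, ending "AND if there are no contraindications to narcotics then randomize". For those who fail: "If patient is ineligible for randomization due to above items then take fentanyl patch off and managed as per usual standard of care".

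Study Procedures also states: "Following enrollment, the schedule of events will be as shown in Figure 1 below". The Data Safety Monitoring Board section treats the period after randomization as starting on day 5.

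**Eligibility.** The criteria are spread over several places:
- Section 3.1 excludes on performance status only "ECOG of 4 and life expectancy ≤ 2 weeks".
- Figure 1, at consent: "There must be no evidence of extensive loculation or hydropneumothorax or other contraindication to pleurodesis or narcotics".
- Figure 1, at day 5 ± 2, requires "ECOG \leq 2 AND patient is now an outpatient" and adds conditions on pain after drainage and on low output with an estimated residual volume of 500 ml or more.
- Figure 2, step 1, has its own consent-stage screen, which adds trapped lung.

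**The concern.** A patient cannot be randomized at catheter placement and then be found ineligible for randomization days later. If staff follow the Study Design sentence, everyone who fails the day-5 check has been allocated but gets no study agent, and no analysis set or rule covers them.

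- **Kept in the analysis:** the failures in the doxycycline arm behave like controls, and the estimated effect shrinks towards no difference.
- **Dropped:** this is exclusion after randomization, at a visit run by the pleurodesis team. Study Procedures lists the patient and the long-term care team as blinded but not the pleurodesis team. Parts of the check, such as the degree of loculation or other contraindications, are matters of judgement. If that team already knew the allocation, it could affect who is excluded.

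Under Figure 1 neither problem arises, because the check comes first.

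The split eligibility criteria add to this. Section 3.1 admits a patient with ECOG 3, whom Figure 1 will not randomize, and it omits loculation, hydropneumothorax and contraindications to narcotics. Yet Study Procedures gives 250 as the number both enrolled and randomized.

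**Working it through.** **1. Which timing does the rest of the plan support?**

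| Place | Randomization point |
|---|---|
| 4.1 Study Design | Immediately after consent, i.e. at catheter placement |
| Figure 1 | Day 5 ± 2, after the check |
| Data Safety Monitoring Board section | Day 5 |
| Statistical Considerations | Ties the drainage variable to the day of the procedure and to the day of randomization, which fits day 5 ± 2 |

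The Study Design sentence is the outlier, but nothing withdraws it.

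**2. The plan's sample size reproduces.** Inputs from Statistical Considerations: hazard ratio (HR) 2.0, two-sided alpha 0.05, power 90%, 1:1 allocation.
- Freedman: (1.960 + 1.282)² × [(2 + 1)/(2 − 1)]² = 94.6, so 95 events, or 96 at 48 per arm. This matches. Schoenfeld, 4 × (1.960 + 1.282)²/(ln 2)², gives 88.
- 96/0.49 = 195.9, so 196 patients; 196/0.90 = 217.8, so 218.
- With 250 randomized, expected events are 250 × 0.90 × 0.49 = 110.

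The arithmetic is sound. It allows for dropout but not for failure at day 5.

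**3. Failures kept.** Let f be the fraction failing at day 5. The documents do not give it; 10, 20 and 30% are assumed, and the screen at consent makes the upper end less likely. A simulation supplied the diluted HR: 250 randomized 1:1; control removal hazard 1.6 per year; true HR 2.0; competing hazard 1.3 per year; one-year follow-up; 10% uniform dropout; a fraction f of the doxycycline arm given the control hazard; Cox model with arm only; 5,000 replicates. The competing hazard gives a one-year control-arm incidence of about 42%, close to the plan's 35.7% (death) + 7.3% (removal for complications or other reasons) = 43.0%. It therefore stands for both, not death alone.

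Analytic power at d = 110 events is Φ(√d × ln HR/2 − 1.96) by Schoenfeld and Φ(√d × (HR − 1)/(HR + 1) − 1.96) by Freedman.

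| f | Observed HR | Simulated events | Simulated power | Schoenfeld, 110 events | Freedman, 110 events |
|---|---|---|---|---|---|
| 0% | 2.01 | 149 | 99% | 95% | 94% |
| 10% | 1.86 | 147 | 96% | 90% | 88% |
| 20% | 1.73 | 145 | 91% | 82% | 80% |
| 30% | 1.61 | 143 | 80% | 71% | 69% |

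The analytic columns use HR 2.0 in the first row. Repeat simulations agreed within about two percentage points.

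**4. Failures dropped.** Events are 250 × (1 − f) × 0.90 × 0.49.

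| f | Patients left | Events | Schoenfeld power at HR 2.0 |
|---|---|---|---|
| 10% | 225 | 99 | 93% |
| 20% | 200 | 88 | 90% |
| 30% | 175 | 77 | 86% |

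Power holds up fairly well here; the concern is bias.

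**5. What 250 counts.** If Figure 1 is followed and 250 counts consents, the 218 in the plan are reached only if 250 × (1 − f) ≥ 218, i.e. f ≤ 12.8%.

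**The case against.** The strongest reply is that the plan is clear once read as a whole. Figure 1, the safety monitoring section and the drainage definition point to day 5, and Study Procedures refers to Figure 1 for the schedule. The harms occur only if staff follow the one outlying sentence. This shows which text should give way, but it does not remove the conflict. The reference to Figure 1 covers events after enrolment, and the Study Design sentence is explicit about timing.

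The sentence might mean only that CORE generates the assignment early and withholds it until day 5. The plan does not say so, and a patient with an assignment would still be called ineligible for randomization. It is fair, though, that the bias argument depends on the pleurodesis team knowing the allocation at the check. The documents do not say when that team learns it, and they call the trial double blind.

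Two-stage eligibility is a normal design, so admitting ECOG 3 at consent and not randomizing such patients is not in itself an error. This stands. The fault is that the stages are not labelled and that one number serves for both enrolled and randomized patients.

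It is also true that the failure rates are assumed and that loss of power alone would not make the point serious. On Freedman's formula, which matches the plan's 96 events, power is one to two points lower than on Schoenfeld's. That changes nothing material.

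**Conclusion.** The concern holds. Two current passages give incompatible randomization points, and no passage reconciles them. This needs correcting because it decides who is in the trial and whether an allocation can exist before eligibility is settled.

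The size depends on an unknown day-5 failure rate. With failures kept, 250 patients hold about 90% power up to roughly 10% failing at the plan's event rate (slightly less on Freedman's formula), or up to roughly 20% in the simulation, which yields more events. These figures assume a true HR of 2.0 and no doxycycline effect in patients who do not receive it. With failures dropped, the risk is selection after allocation, which the documents do not allow one to quantify.

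**What to change.** Replace the Study Design sentence with: *Randomization in CORE takes place at the day 5 ± 2 visit, after the Figure 1 eligibility check is recorded and before instillation; 250 patients will be randomized and all are analysed in their assigned arm.* This also settles which day is meant by the day of randomization for the 150 ml cut-off.

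Two related statements should be aligned at the same time. State the time origin for time to removal, since Study Procedures counts follow-up from catheter placement. Limit the statement that patients at the extra visit receive doxycycline or saline to those randomized.

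Merge Section 3.1, the two stages of Figure 1 and Figure 2 step 1 into one eligibility list, each criterion marked as applying at consent or at day 5 ± 2. The criteria to reconcile include ECOG, loculation and hydropneumothorax, trapped lung, and contraindications to narcotics. Which clinical thresholds apply is for the investigators; this review takes no position.

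The editing cost is small, because Figure 1 already provides the visit and the checks. The practical cost is that some patients consent but are never randomized. To randomize 250, consents needed are 250/(1 − f): about 278 if 10% fail and 313 if 20% fail.

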For the primary outcome, assuming a Hazard ratio of 2.0 for time to removal of doxycycline vs. conventional treatment and a 1:1 ratio of IPC + doxycycline: conventional IPC patients, then to have 90% power to detect a difference with a two-sided alpha set at 0.05 will require 48 events in each arm (total events=96). The lower border of the 95% CI for catheter removal from our prior study of IPCs was 49%. So if only 49% of patients have their catheter removed for decreased drainage then this will require 196 patients to be enrolled. If 10% of patients drop out then a total of 218 patients will need to be enrolled to generate the 196 patients that will generate 96 events (i.e. catheter removals). We expect dropout rates to be low based on our prior observational study and because the only difference in the intervention arm is a single visit at day 5. Everything else is standard of care. We will be conservative and enroll 250 patients.

Secondary outcomes for pleural fluid recurrence and quality adjusted survival are really exploratory, since the number of events and the magnitude of the effect are likely to be small. For pleural fluid recurrence following catheter removal, we only expect 14% of patients to develop recurrence requiring drainage. Since we have powered the study to have 96 catheter removals, we expect only 14 patients to have fluid recurrence requiring additional intervention. For the secondary outcome of quality-adjusted survival (measured as QALYs), we expect baseline utility to be approximately 0.6 based on our prior study.⁸ In prior multivariate analysis the factors impacting change in utility were chemotherapy or radiation after IPC and severity of baseline dyspnea. Patients with more dyspnea experienced greater improvement in quality adjusted survival since the procedure improved their condition more dramatically. We will use the Kaplan-Meier product-limit method to estimate median QALYs following IPC placement. We will use paired t-test to compare baseline and 1-month Borg scores and utilities. A generalized linear model will be used to evaluate whether other variables have any impact on the pairwise differences between baseline and 1 month.

Data Safety Monitoring Board

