3. Give them a fentanyl patch 12 mcg/hour to take home. This is to be placed on day 5 +/- 2 ideally in the morning upon waking up prior to f/u appoint since it takes time to have effect
4. Patient comes in for scheduled visit on day 5 +/- 2 for CXR and then to CPC clinic and is assessed by MLP. Baseline SF6D, pain instrument, Borg as per usual standard. Assuming no dramatic change or infection then goes to procedure area. Nurse places IV.
5. Give pain control with Fentanyl 50 mcg at start of IPC procedure
6. Drain pleural fluid as per usual standard of care until pain or cough.
7. Reassess patient and pain control and give one additional dose of fentanyl 25 mcg if pain VAS 5-7 or fentanyl 50 mcg if VAS is 8-10. If pain level on VAS is 0 – 4 no additional fentanyl is needed.
8. Instill pleurodesis agent (e.g. Doxycycline 500 mg dissolved in 50 ml of normal saline + 25 ml of 1% lidocaine (250 mg))
9. Cap for 1 hour, giving additional doses of fentanyl 25 mcg if pain VAS 5-7 or fentanyl 50 mcg if VAS is 8-10. If pain level on VAS is 0 – 4 no additional fentanyl is needed.
10. If pain control is not adequate, defined as a VAS of 7-10, while in the clinic following IPC after fentanyl total dose is 150 mcg or if there is doubt about maintenance of control then patient goes to pain clinic on the 4th floor for walk in appointment prior to discharge. Pulmonary attending or MLP places consult to pain clinic in orders. Pulmonary recovery area nurse is to put in an online consult and calls the pain clinic at [name] to notify them patient is coming gives hand/off sign out. If there are problems regarding availability then nurse can speak to pain clinic supervisor, [name]. If there is no availability in pain clinic for walk in then the back-up is to send them to EC and have the inpatient pain service come to see as a consult. If this occurs, please place typed note in clinic station using IPC template, delineating need for pain control.
11. If pain control is good, defined as a VAS of 0-4, patient and family receive instruction on pain control algorithm and patient goes home on Hydrocodone 5 mg with acetaminophen 325 mg tablets every 4 hours PRN, dispense 28 tablets (7 days) in addition to the fentanyl patch placed previously. Fentanyl patch should be taken off in 3 days. Follow-up care is as per usual IPC protocol.

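### The quality-adjusted survival analysis leaves out baseline SF-6D and Borg, which are already collected; adjusting for them is a modest, free gain in precision for an exploratory outcome

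*Combined protocol and SAP*

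**What the plan says.** Section 4.1, Study Design, lists quality-adjusted survival as a secondary outcome, obtained by deriving utilities from the SF-6D and then "integrating utilities over time to arrive at quality-adjusted survival". Statistical Considerations includes it among the outcomes meant to show how the intervention works, so a comparison of arms is evidently intended.

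The one QALY method named there is: "We will use the Kaplan-Meier product-limit method to estimate median QALYs following IPC placement". No between-arm test, model or covariate follows. Two further sentences deal with change at 1 month: "We will use paired t-test to compare baseline and 1-month Borg scores and utilities", and "A generalized linear model will be used to evaluate whether other variables have any impact on the pairwise differences between baseline and 1 month". That model does not list its covariates and is not applied to QALYs. The covariate and interaction analyses planned elsewhere in the section concern catheter removal. Study Design states no stratification factor.

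On baseline values, the plan says "we expect baseline utility to be approximately 0.6 based on our prior study" and gives no SD. From the prior cohort it reports: "Patients with more dyspnea experienced greater improvement in quality adjusted survival since the procedure improved their condition more dramatically". Figure 2 records SF-6D and Borg twice before instillation: at consent (step 1) and again at the day 5 visit (step 4, "Baseline SF6D, pain instrument, Borg as per usual standard"). The plan itself calls the QALY outcome exploratory and attaches no power to it.

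**The concern.** A QALY total is the area under a patient's utility curve. A patient who starts higher, and tends to stay higher, collects more QALYs whatever the treatment does. If the arms differ by chance in starting utility, part of that difference reappears in the QALY comparison. Variation in starting utility also adds to its standard error. Regression on the baseline value removes the first and reduces the second, and the baseline values are already being recorded.

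At stake is how well the trial measures an effect that the plan expects to be small. Writing the adjustment down beforehand also prevents a choice between adjusted and unadjusted results once the data are seen.

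**Working it through.** **The plan's figures.** There is no sample size, SD or effect size for QALYs to reproduce. The primary-outcome figures (96 removals; 96/0.49 = 195.9, so 196; 196/0.9 = 217.8, so 218; 250 enrolled) are unaffected by this point. From them I take only 250/2 = 125 per arm.

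**Inputs.** From the documents: mean utility 0.6, 125 per arm, at least 1 year of follow-up. Assumed, because the documents are silent: utility SD σ = 0.10-0.15, baseline-to-later correlation ρ = 0.3-0.7, exponential survival with median 5-9 months, no treatment effect, and full follow-up to 1 year. The quantity is the mean QALY to 1 year, Q = later utility × T, with T the survival time in years capped at 1.

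**Chance imbalance.** The SE of the between-arm difference in mean baseline utility is σ√(2/125) = 0.1265σ, that is 0.0126 (σ = 0.10) or 0.0190 (σ = 0.15). Two SEs are 0.025 or 0.038. About 5% of trials exceed 2 SEs, so this is a large imbalance.

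**Formulas when utility does not predict death.** With λ = ln 2 / median (years):

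- E[T] = (1 − e^−λ)/λ, and E[T²] = 2[1 − e^−λ(1 + λ)]/λ²
- Var Q = (0.6² + σ²)E[T²] − 0.6²E[T]²
- SE of the unadjusted QALY difference = SD(Q) × 0.1265
- shift = baseline gap × ρ × E[T]
- r = correlation of baseline utility with Q = ρσE[T]/SD(Q)
- gain in effective patients = 1/(1 − r²) − 1

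| | Low corner | High corner |
|---|---|---|
| Median, σ, ρ | 5 months, 0.10, 0.3 | 9 months, 0.15, 0.7 |
| λ | 1.664 | 0.924 |
| E[T], E[T²] | 0.487, 0.358 | 0.653, 0.553 |
| SD(Q) | 0.217 | 0.242 |
| SE of difference | 0.027 | 0.031 |
| Shift at 2 SE | 0.025 × 0.3 × 0.487 = 0.004 | 0.038 × 0.7 × 0.653 = 0.017 |
| r | 0.067 | 0.284 |
| Gain | 0.5% | 9% |

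The shift divided by the SE is simply 2r, so these rows restate one assumed correlation and are not separate evidence. For a median-sized imbalance (0.67 SE) the shift is 0.67r of the SE: 0.67 × 0.067 = 4% to 0.67 × 0.284 = 19%.

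**A variant.** A simulation let mean utility move from 0.6 to 0.65 over the first month and took median survival of 4-12 months, with the same σ and ρ ranges. The 95% range of the carried difference was ±0.004 to ±0.020, the SE was 0.027-0.033, and adjustment lowered the SE by 0.2-5%. Survival time dominates the variance of QALYs.

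**If utility also predicts death.** With an assumed hazard ratio of 0.75 per SD of utility, simulation puts the gain at about 8-24%, which corresponds to r of about 0.27-0.44 (1/(1 − 0.27²) − 1 = 8%; 1/(1 − 0.44²) − 1 = 24%).

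**Not quantified.** The documents do not allow a figure for Borg. The calculation covers the 1-year mean and does not carry over directly to the plan's Kaplan-Meier median.

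**The case against.** The strongest reply is that nothing here is wrong in the sense of being invalid. With randomisation, baseline imbalance is random error, and a properly calculated unadjusted interval already allows for it. The outcome is exploratory, no sample size rests on it, and the gain may be as low as 0.5%. All of that stands, and it limits the point to precision and to imbalance in the particular trial observed.

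Three stronger readings are tempting, and the documents do not support them.

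- A reader might infer that baseline dyspnea was shown to determine quality-adjusted survival. The plan ties dyspnea to change in utility and to improvement. If more breathless patients gain more, baseline differences could shrink over follow-up and carry over less, which is why ρ is taken down to 0.3.
- A reader might infer that future power calculations will rest on the QALY result. The Data Safety Monitoring Board text gives time to fluid recurrence as its example and does not name QALYs.
- A reader might take the upper figures (8-24%) as expected. They need baseline utility to predict death, which no section says.

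It is also fair to say that a more basic gap comes first: no between-arm QALY comparison is specified, so there is not yet one to adjust. That supports settling both in the same sentence.

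**Conclusion.** The omission is real and minor. No section plans to use baseline SF-6D or Borg in the QALY analysis, and the generalized linear model for 1-month change does not fill the gap. The result is some lost precision and uncorrected chance imbalance in an exploratory outcome. Any QALY difference would not be systematically biased.

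Even a large baseline gap moves the 1-year mean difference by roughly 13-57% of one standard error (2r, with r = 0.067-0.284), and a typical gap by much less. The efficiency gain is a few percent under most of the assumed inputs. These sizes rest entirely on assumed SDs, correlations and survival. The case for acting is that the improvement is free, not that the harm is large.

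**What to change.** In Statistical Considerations, name the between-arm QALY comparison as the difference in mean QALYs restricted to 1 year from IPC placement. Estimate it by a regression on treatment, baseline SF-6D utility and baseline Borg that allows for censoring, for example with inverse-probability-of-censoring weights or pseudo-values. Ordinary regression is not enough: follow-up is planned for at least 1 year, but the plan allows for 10% drop-out, and those QALYs would be cut short.

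Define baseline as the consent-day (IPC placement) values. QALYs are counted from IPC placement, so the day 5 measurement already lies inside the integrated curve. Report the unadjusted difference beside the adjusted one. The Kaplan-Meier median can stay as a description.

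This is a free improvement. It needs no new data, visits or patients, and the only cost is a little more analysis work.
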